5.3. Analysis populations

Participants will be analysed in the treatment group to which they were randomised, regardless of treatment compliance. Analysis populations will be as follows:

- Primary outcome, live birth at or beyond 34 weeks: all randomised participants. Analyses will also be produced using women who achieved pregnancy, defined as a positive pregnancy test (urine or serum beta-hCG test >10 mIU/ml), as the denominator but this will be treated as supportive evidence only)
- Secondary outcomes:
 - (Treatment outcomes) Ovulation rate, time from randomisation to pregnancy: all randomised participants
 - (Treatment outcomes) Number of ovulation induction cycles required for pregnancy: women who achieved pregnancy (defined as a positive pregnancy test (urine or serum beta-hCG test >10 mIU/ml))
 - (Pregnancy end outcomes) Ongoing pregnancy at 12 weeks (range 11⁺⁰ to 14⁺⁰ weeks) of gestation, pregnancy loss (defined as pregnancy loss <24 weeks of gestation), termination, stillbirth, molar pregnancy, pregnancy of unknown location, ectopic pregnancy, multiple live births: all randomised participants (analyses will also be produced using women who achieved pregnancy, defined as a positive urine or serum beta-hCG test >10 mIU/ml, as the denominator but this will be treated as supportive evidence only)
 - Time from conception to delivery (gestational age at live birth), gestational age <28/<32/<37 weeks, singleton live births at and beyond 34 completed weeks of gestation, live births at and beyond 37 completed weeks of gestation, mode of birth (unassisted vaginal, instrumental vaginal, elective caesarean section, emergency caesarean section, vaginal breech birth, other), number of ovulation induction cycles to live birth ≥24 weeks : women with live birth ≥24 weeks
 - Birth weight, APGAR score (at 1, 5 and 10 minutes) and APGAR score <7 out of 10 (at 1, 5 and 10 minutes): babies born alive ≥24 weeks
 - Antenatal outcomes: women achieving pregnancy
 - o Intrapartum outcomes: women with live birth≥24 weeks
 - Post-partum outcomes: women with live birth≥24 weeks
 - Maternal outcomes: all randomised participants

- Neonatal outcomes: babies born alive ≥24 weeks.
- Survival at 28 days of neonatal life: babies born alive ≥24 weeks
- Safety outcomes:
 - \circ Neonatal congenital or chromosomal abnormalities: babies born alive ≥24 weeks

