   Singleton live births at and beyond 34 completed weeks of gestation
CRF: LOCI: 05. Pregnancy Booking Scan Form
Question:
   • 'Number of fetus(es)?' = 1
CRF: LOCI: 07. Pregnancy Outcome Form
Question:
     'Was the baby born alive?' = Yes
   0
AND
   ◦ 'Gestation at pregnancy end:' = \geq34 weeks
  Live births at and beyond 37 completed weeks of gestation
•
CRF: LOCI: 07. Pregnancy Outcome Form
Question:
   \circ 'Was the baby born alive?' = Yes
AND
     'Gestation at pregnancy end:' = \geq 37 weeks
   0
```

```
Mode of birth (unassisted vaginal, instrumental vaginal, elective caesarean
٠
   section, emergency caesarean section, vaginal breech birth, other)
CRF: LOCI: 07. Pregnancy Outcome Form
Question:
   \circ 'Was the baby born alive?' = Yes
AND
      'Gestation at pregnancy end:' = \geq24 weeks
   0
AND
     'Mode of birth' = unassisted vaginal, instrumental vaginal, elective caesarean section,
   0
      emergency caesarean section, vaginal breech birth, other
   Birth weight
•
CRF: LOCI: 07. Pregnancy Outcome Form
Question:
   \circ 'Was the baby born alive?' = Yes
AND
   ◦ 'Gestation at pregnancy end:' = \geq24 weeks
AND
     'Birth weight'
   0
   APGAR score <7 out of 10 (at 1, 5 and 10 minutes)
CRF: LOCI: 07. Pregnancy Outcome Form
Question:
   0
     'Was the baby born alive?' = Yes
AND
      'Gestation at pregnancy end:' = \geq24 weeks
   0
AND
   • 'Appar at 1 minute:' = <7
   • 'Apgar at 5 minutes:' = <7
   • 'Apgar at 10 minutes:' = <7
```

Antenatal outcomes:

Antepartum haemorrhage **CRF:** LOCI: 07. Pregnancy Outcome Form **Question:** \circ 'Was the baby born alive?' = Yes AND 'Antepartum haemorrhage?' = Yes 0 **CRF:** LOCI: 08. Maternal Outcome Form **Question:** • 'Did the woman suffer antepartum haemorrhage?' = Yes Pregnancy-induced hypertension • **CRF:** LOCI: 07. Pregnancy Outcome Form **Question:** \circ 'Was the baby born alive?' = Yes AND • 'Hypertension / pre-eclampsia?' = Yes CRF: LOCI: 08. Maternal Outcome Form **Question:** \circ 'Did the woman suffer pregnancy induced hypertension?' = Yes Pre-eclampsia CRF: LOCI: 07. Pregnancy Outcome Form **Question:** \circ 'Was the baby born alive?' = Yes AND 'Hypertension / pre-eclampsia?' = Yes 0 CRF: LOCI: 08. Maternal Outcome Form **Question:** \circ 'Did the woman suffer pre-eclampsia?' = Yes **Obstetric cholestasis** •

CRF: LOCI: 08. Maternal Outcome Form **Question**:

 \circ 'Did the woman suffer obstetric cholestasis?' = Yes

```

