Preterm (<37 weeks) pre-labour rupture of membranes
٠
CRF: LOCI: 07. Pregnancy Outcome Form
Question:

    `Was the baby born alive?' = Yes

AND
     'Gestation at pregnancy end:' = <37 weeks
   0
AND
      'Pre-PROM?' = Yes
   0
CRF: LOCI: 08. Maternal Outcome Form
Question:
   \circ 'Did the woman suffer preterm (<37 weeks) pre-labour rupture of membranes?' = Yes
   Gestational diabetes
CRF: LOCI: 07. Pregnancy Outcome Form
Question:
   \circ 'Was the baby born alive?' = Yes
AND
     'Gestational diabetes mellitus / type I diabetes / type II diabetes?' = Yes
   0
CRF: LOCI: 08. Maternal Outcome Form
Question:
   \circ 'Did the woman suffer gestational diabetes, diagnosed by GTT?' = Yes
Intrapartum outcomes:
   Chorioamnionitis
CRF: LOCI: 07. Pregnancy Outcome Form
Question:
   \circ 'Was the baby born alive?' = Yes
AND
       'Were there any intrapartum complications?' = Yes
   0
AND
   \circ 'Chorioamnionitis?' = Yes
```

```
Fetal growth restriction
•
CRF: LOCI: 07. Pregnancy Outcome Form
Question:

    Suspected IUGR = Yes

  Macrosomia
•
CRF: LOCI: 07. Pregnancy Outcome Form
Question:
     'Was the baby born alive?' = Yes
   0
AND
      'Fetal macrosomia?' = Yes
   0
Post-partum outcomes:
  Haemorrhage
•
CRF: LOCI: 08. Maternal Outcome Form
Question:
   • 'Did the woman suffer any other complications?'= Yes
AND
     'Haemorrhage?' = Yes
   0
Maternal outcomes:
   Admission to high dependency unit (HDU)
•
```

CRF: LOCI: 08. Maternal Outcome Form

Question:

 $_{\odot}$ `Was the participant admitted to HDU (level 2 care) prior to post-natal discharge?'= Yes

• Admission to intensive therapy unit (ITU)

CRF: LOCI: 08. Maternal Outcome Form **Question:**

 $_{\odot}$ `Was the participant admitted to ITU (level 3 care) prior to post-natal discharge?'= Yes

Neonatal outcomes:

Discharge to hospital

```
CRF: LOCI: 07. Pregnancy Outcome Form
Question:
• 'Was the baby born alive?' = Yes
```

AND

• 'Was the baby discharged from hospital? = Yes

AND

- 'Discharged to' = 'Other hospital'
 - Early infection

```
CRF: LOCI: 07. Pregnancy Outcome Form Question:
```

```
\circ 'Was the baby born alive?' = Yes
```

AND

• 'Early infection'= Yes

Retinopathy of prematurity

CRF: LOCI: 07. Pregnancy Outcome Form **Question:**

• 'Was the baby born alive?' = Yes

AND

• 'Retinopathy of prematurity requiring treatment?' = Yes

• Necrotising enterocolitis

CRF: LOCI: 07. Pregnancy Outcome Form **Question:**

 \circ 'Was the baby born alive?' = Yes

AND

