• Insulin resistance confirmed clinically or laboratory testing (yes and no) confirmed as yes if:

• 'Does the woman suffer from type 2 diabetes?' = Yes (LOCI: 02. Baseline Medical

Details Form)

- OR
 - Other relevant medical history?' = Yes AND 'Diabetes' = Yes (LOCI: 02. Baseline Medical Details Form)

OR

`Onset of labour' = Induced AND `Gestational diabetes mellitus / type I diabetes / type II diabetes?' = Yes AND `If yes to Gestational diabetes, please provide GTT:' >7.8 mmol/L (LOCI: 07. Pregnancy Outcome Form)

OR

 Did the woman suffer gestational diabetes, diagnosed by GTT?' = Yes (LOCI: 08. Maternal Outcome Form)

OR

`Has the participant previously had HbA1c concentrations measured?' = Yes AND `HbA1c'
 <48.0 mmol/mol (LOCI: 02. Baseline Medical Details Form)

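### SAP 9.4 gives no rule for combining Forms 07 and 08 for pregnancy-induced hypertension and pre-eclampsia, which share one Form 07 box, and leaves macrosomia and growth restriction undefined.

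*SAP*

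**What the plan says.** **Hypertensive outcomes (SAP 9.4, antenatal outcomes).** Under pregnancy-induced hypertension the SAP lists two sources. The first is Form 07: baby born alive, and a Yes to "Hypertension / pre-eclampsia". The second is Form 08: a Yes to "Did the woman suffer pregnancy induced hypertension". Under pre-eclampsia the Form 07 condition is repeated unchanged, and the Form 08 item is "Did the woman suffer pre-eclampsia". AND is written between the items within Form 07. Nothing is written between the Form 07 block and the Form 08 block.

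**Denominator (SAP 5.3).** "Antenatal outcomes: women achieving pregnancy".

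**Fetal size (SAP 9.4, intrapartum outcomes).** Fetal growth restriction is "Suspected IUGR = Yes". Macrosomia is a Yes to "Fetal macrosomia" with the baby born alive. Both come from Form 07 only, with no weight, centile or other definition. The same form holds gestation at pregnancy end and birth weight. SAP 5.3 sets the population for birth weight in a line that ends "APGAR score <7 out of 10 (at 1, 5 and 10 minutes): babies born alive ≥24 weeks".

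**The concern.** Two conditions that the trial lists as separate outcomes share an input that cannot tell them apart. Whether this matters depends on a join that the SAP leaves open, so two programmers could follow 9.4 faithfully and produce different case counts from the same data. If the choice is made after the allocation is known, it can also be made with the results in view.

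For fetal size, a recorded suspicion and an undefined Yes/No box depend on local practice. A reader of the trial report could not say what was counted, although weight and gestation are available to describe size at birth objectively.

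At stake are the event rates and relative risks for hypertensive disease, and the interpretability of the fetal size results, in all the trial comparisons.

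**Working it through.** The documents give no event rate, power or target for these outcomes, so there is no plan figure to reproduce. The check is a reading of the rules followed by an illustration.

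**Step 1: which join does 9.4 imply?** Its own usage points both ways.
- For singleton live births (Forms 05 and 07), twin live births (Forms 05 and 07) and cycles to live birth (Forms 04 and 07), forms are stacked with no connective, and AND is plainly meant.
- In the insulin resistance subgroup, the Form 07 diabetes condition and the Form 08 gestational diabetes item are joined by a written OR.
- Obstetric cholestasis uses Form 08 alone.

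**Step 2: consequence of each rule.**
- OR: a woman with hypertension only ticks the shared box and becomes a pre-eclampsia case. A woman with pre-eclampsia only becomes a pregnancy-induced hypertension case.
- AND: the Form 08 item keeps the two conditions apart, but the live-birth condition in the Form 07 block then applies to every case. A woman with pre-eclampsia and a stillbirth stays in the 5.3 denominator as a non-case. A case not ticked on Form 07 is also lost.
- Form 08 alone: neither problem arises.

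**Step 3: illustrative size under OR.** These inputs are all assumptions, none from the documents: control pre-eclampsia P = 3–5%; other hypertension H = 4–8%; the two do not overlap; Form 08 is correct; all these women have a live birth; true relative risk (RR) 0.50 for pre-eclampsia and 1.00 for other hypertension. Let c be the share of cases for whom the Form 07 box is ticked.

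Reported pre-eclampsia RR = (0.5P + cH) / (P + cH). With c = 1:

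| P | H | Control, derived | Treated, derived | Reported RR | True share of control cases |
|---|---|---|---|---|---|
| 3% | 4% | 7% | 5.5% | 0.79 | 3/7 = 43% |
| 3% | 8% | 11% | 9.5% | 0.86 | 3/11 = 27% |
| 5% | 4% | 9% | 6.5% | 0.72 | 5/9 = 56% |
| 5% | 8% | 13% | 10.5% | 0.81 | 5/13 = 38% |

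The range is 0.72–0.86 against a true 0.50. With c = 1 the two derived outcomes are the same variable, so pregnancy-induced hypertension also shows 0.72–0.86, although its true RR is 1.00.

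With c = 0.3 the distortion shrinks:
- P = 5%, H = 4%: (2.5 + 1.2) / (5 + 1.2) = 0.60.
- P = 3%, H = 8%: (1.5 + 2.4) / (3 + 2.4) = 0.72.

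**Step 4: AND.** If the loss of cases is the same in both arms, the RR stays at 0.50 and only the rate falls. At P = 5% and c = 0.3 the derived rate is 0.3 × 5% = 1.5%.

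**Step 5: fetal size.** The 5.3 population for intrapartum outcomes is women with a live birth at or beyond 24 weeks. Birth weight and gestation are collected for babies in that range, yet neither enters the macrosomia or growth restriction rule. I give no size here, because the documents say nothing about how well the tick boxes perform.

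**The case against.** The strongest reply is that the SAP does not rely on the shared box alone. The condition-specific Form 08 item is inside each derivation, and 9.4 tends to write OR where it means OR, so AND is arguably the natural reading, and AND keeps the conditions separate. This stands in part. A reader might infer that pre-eclampsia and pregnancy-induced hypertension are one variable under this plan; the text does not show that. What is shown is an unstated join with a defect on either side.

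Four further inferences go beyond the documents:
- **All four outcomes are mismeasured.** For the hypertensive pair this depends on the join. For fetal size, the documents show an undefined measure and not a wrong one.
- **Form 07 boxes are completed only when labour is induced.** The insulin resistance definition pairs "Onset of labour' = Induced AND `Gestational diabetes mellitus" on Form 07, which invites this. The form is not in the documents, so the point cannot be relied on.
- **Birth weight should replace the growth restriction item.** Small size at birth is a different construct from the named outcome, and birth weight and gestational age are already analysed in their own right. Birth weight supports a supplementary analysis only, and only for live births at or beyond 24 weeks.
- **Treatment alters scanning, and so suspicion.** Nothing in the documents bears on this.

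The reply on importance also stands. The protocol classes these outcomes as exploratory and leaves them untested (8.1.3.2 and 13.2). SAP 5.1 gives secondary outcomes confidence intervals and names p-values only for the primary and safety outcomes. Attending clinicians are blinded (SAP 4.1), so recording errors should be similar between arms.

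**Conclusion.** The concern holds as a gap in the derivation rules. The plan does not say how Forms 07 and 08 combine for pregnancy-induced hypertension and pre-eclampsia. OR mixes the two conditions; AND drops cases without a live birth from the numerator while 5.3 keeps those women in the denominator. Form 08 alone avoids both.

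The figure of 0.72–0.86 for a true 0.50 applies only to OR, a fully completed box and the assumed rates. It shrinks as box completion falls, and mixing does not occur under AND. The likely harm is dilution of an effect specific to one condition, its leakage into the other, and wrong absolute rates.

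Macrosomia and growth restriction are undefined as written, with no demonstrated bias. The primary outcome is untouched. The repair is cheap and worth making before the statistician is unblinded.

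**What to change.** - In SAP 9.4, derive pregnancy-induced hypertension and pre-eclampsia each from its own Form 08 item only, as is already done for obstetric cholestasis. If the Form 07 box is reported at all, label it any hypertensive disorder.
- Confirm that Form 08 is completed for pregnancies without a live birth. The SAP already takes OHSS and HDU/ITU admission from it with all randomised women as the denominator, which suggests that it is.
- State the source or join for the other antenatal outcomes with the same two-form layout: antepartum haemorrhage, preterm pre-labour rupture of membranes and gestational diabetes.
- Keep the prespecified macrosomia and growth restriction items. Add two supportive analyses in babies born alive at or beyond 24 weeks: macrosomia by a stated birth-weight cut-off, and a separately named small-for-gestational-age outcome from a named reference chart.

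The cost is a few lines of SAP text and some programming, with no new data collection. The downside is that a cut-off and a chart must be chosen and named, which should be done before unblinding.

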• Insulin resistance confirmed clinically or laboratory testing (yes and no) confirmed as yes if:

• 'Does the woman suffer from type 2 diabetes?' = Yes (LOCI: 02. Baseline Medical

Details Form)

- OR
 - Other relevant medical history?' = Yes AND 'Diabetes' = Yes (LOCI: 02. Baseline Medical Details Form)

OR

`Onset of labour' = Induced AND `Gestational diabetes mellitus / type I diabetes / type II diabetes?' = Yes AND `If yes to Gestational diabetes, please provide GTT:' >7.8 mmol/L (LOCI: 07. Pregnancy Outcome Form)

OR

 Did the woman suffer gestational diabetes, diagnosed by GTT?' = Yes (LOCI: 08. Maternal Outcome Form)

OR

`Has the participant previously had HbA1c concentrations measured?' = Yes AND `HbA1c'
 <48.0 mmol/mol (LOCI: 02. Baseline Medical Details Form)

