9.9. Planned subgroup analyses

Subgroup analyses will be restricted to the primary outcome only. BMI (<30 and \geq 30 kg/m²) is the single key subgroup of interest (i.e. we propose to be able to draw firm conclusion about any differential effect with respect to this variable only). The following subgroup analyses will be considered exploratory:

From the minimisation algorithm -

- Maternal age (<35 and ≥35 years);
- Body mass index (<30 and \geq 30 kg/m²);
- Any previous pregnancy (yes and no);
- Previous exposure to either clomifene or letrozole;
- Any menstrual periods in the preceding 6 months (yes and no);

As well as the following variables –

- Ethnicity (White/South Asian/Black/Other)
- History of previous miscarriage $(0/1-2/\geq 3)$
- Androgen excess confirmed clinically or through laboratory testing (yes and no) see section 9.4 Data manipulations on derivation details
- Insulin resistance confirmed clinically or laboratory testing (yes and no) see section 9.4 Data manipulations on derivation details.

Tests for interaction will be performed by including the treatment group by subgroup interaction parameter in the statistical model. A p-value for this parameter will be produced. Given there is only one key subgroup of interest, no adjustments will be made for multiple testing on this p-value.

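### The exploratory insulin-resistance subgroup codes HbA1c in the wrong direction and takes two of its five criteria from after conception, so its relative-risk interaction test is not valid as written

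*SAP*

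**What the plan says.** SAP 9.9 lists "Insulin resistance confirmed clinically or laboratory testing (yes and no") among the exploratory subgroups and refers to SAP 9.4 for its derivation. There the flag is yes if any one of five conditions holds:

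- type 2 diabetes at baseline ("Does the woman suffer from type 2 diabetes?' = Yes", form 02);
- diabetes in the medical history (form 02);
- induced labour, with diabetes recorded and a raised glucose tolerance test ("please provide GTT:' >7.8 mmol/L (LOCI: 07. Pregnancy Outcome Form"));
- gestational diabetes ("Did the woman suffer gestational diabetes, diagnosed by GTT?' = Yes (LOCI: 08. Maternal Outcome Form"));
- HbA1c previously measured, with a value "<48.0 mmol/mol (LOCI: 02. Baseline Medical Details Form").

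SAP 9.9 also says: "Subgroup analyses will be restricted to the primary outcome only". It tests each subgroup through an interaction term and reports a p-value. SAP 9.5 gives the primary outcome a denominator of all women randomised. SAP 4.4 lists gestational diabetes as a secondary antenatal outcome, and SAP 5.3 gives its population: "Antenatal outcomes: women achieving pregnancy".

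Insulin resistance is not among the subgroups in protocol 13.2.3, so SAP 9.4 is its only definition.

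**The concern.** There are two separate defects.

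**Direction.** Four conditions treat diabetes or high glucose as evidence of insulin resistance, while the HbA1c condition treats a low value as evidence. Because the conditions are joined by OR, one non-diabetic HbA1c result puts a woman in the yes group whatever else is recorded. On HbA1c alone, a woman at or above the cut-off is not flagged.

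**Timing.** The form 07 and form 08 conditions arise after randomisation and require a pregnancy; the form 07 condition also requires labour. A woman who never conceives cannot enter the yes group by these routes. Membership therefore depends on the outcome being compared. Metformin or placebo continues to 14 completed weeks of pregnancy (SAP 4.2), so allocation might also influence who is diagnosed with gestational diabetes.

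An interaction test on such a flag can show effect modification where there is none. The result would be reported with a p-value under a label that the variable does not measure.

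**Working it through.** **Inputs from the documents.** Live birth 39% vs 29%, and 1,520 women analysed, 760 per group (SAP 4.7). These reproduce the plan's power: a two-sided 5% test of two proportions with pooled variance gives 98.5%, as stated. The documents give no prevalence, size or power for this subgroup.

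**Assumptions, not in the documents.** *b* is the share of women flagged by baseline criteria, unrelated to outcome. *g* is the share of live births with gestational diabetes. *m* is the share with an HbA1c result, and *l* is the share of those results below 48.

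**Step 1, HbA1c direction.** Women flagged by the written rule = 1,520 × m × l; by the reversed rule = 1,520 × m × (1 − l).
- Written rule: from 1,520 × 0.20 × 0.90 = 274 to 1,520 × 0.80 × 0.99 = 1,204.
- Reversed rule: from 1,520 × 0.20 × 0.01 = 3 to 1,520 × 0.80 × 0.10 = 122.

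As written, the condition mostly records that a woman had a non-diabetic test result.

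**Step 2, post-randomisation criteria with no true modification.** With live-birth rate p in an arm:
- rate in yes = [b·p + (1 − b)·p·g] / [b + (1 − b)·p·g]
- rate in no = p(1 − g) / (1 − p·g)

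For b = 0.05 and g = 0.20:
- yes: 0.0936/0.1241 = 75.4% vs 0.0696/0.1051 = 66.2%, RR 1.14
- no: 0.312/0.922 = 33.8% vs 0.232/0.942 = 24.6%, RR 1.37
- ratio of RRs 1.139/1.374 = 0.83, where the truth is 1.00 (RR 1.345 in both strata)

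| Baseline flag b | Ratio of RRs, g = 20% | Ratio of RRs, g = 10% |
|---|---|---|
| 5% | 0.83 | 0.88 |
| 20% | 0.92 | 0.96 |
| 40% | 0.95 | 0.98 |
| 60% | 0.97 | 0.98 |
| 80% | 0.97 | 0.99 |

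Over b from 2% to 20% and g from 5% to 30%, the ratio runs from 0.76 to 0.98. Allowing gestational diabetes in women without a live birth, at 5% of the rate in live births, changes 0.83 to 0.84.

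**Step 3, both defects together.** Take l = 95% and another 5% of women flagged by other baseline criteria. The flag is then 1 − (1 − 0.95m)(0.95), which is 23% at m = 20% and 77% at m = 80%. With g = 20% the ratio of RRs is 0.93 and 0.97.

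**Step 4, risk difference.** In the step 2 example it is 9.2 points in each stratum (75.4 − 66.2 and 33.8 − 24.6), against a true 10.

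**Step 5, metformin with no effect on live birth (34% in both arms).** Let b = 0.05, with gestational diabetes in 20% of live births on placebo.
- Halved to 10% on metformin: yes 0.0493/0.0823 = 59.9% vs 0.0816/0.1146 = 71.2%, RR 0.84; no 0.306/0.966 = 31.7% vs 0.272/0.932 = 29.2%, RR 1.09.
- Reduced only to 16%: RRs 0.95 and 1.03.
- With b = 0.40: RRs 0.93 and 1.09 if halved, 0.97 and 1.03 if reduced to 16%.

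**Step 6, how often it would show.** With 760 per group, a Wald test on the log ratio of RRs in the step 2 example reaches p < 0.05 about 30% of the time. At a 40% flag it does so about 6% of the time, close to the nominal 5%.

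**The case against.** The best case on the other side is about size and reach, and most of it stands.

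- **Exploratory status.** SAP 9.9 reserves firm conclusions for BMI. No primary comparison, key subgroup or power figure uses this flag, and SAP 1 allows deviations if they are documented. A reader might infer that the trial's answer is at risk; the documents do not support that.
- **The two defects do not add up.** A reader might take 0.83 as the expected bias and suppose that the HbA1c reversal makes it worse. That figure assumes a 5% baseline flag, which leaves out the HbA1c rule as written. If that rule flags many women, it dilutes the gestational-diabetes distortion. This does not rescue the subgroup, because the yes group then no longer means insulin resistant.
- **Scale.** A reader might infer that every treatment-effect estimate in the subgroup will be wrong. When gestational diabetes is equally common in both arms, the bias is mainly on the relative scale, and the risk difference may move little.
- **Opposite effects of metformin.** These require metformin to change gestational diabetes, by an amount the documents do not give. It is a possibility, not a prediction.
- **Extraction error.** An inequality sign altered in reading the PDF cannot be fully excluded. The neighbouring GTT sign and those in the androgen-excess definition read correctly, so it is unlikely.

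None of this answers the two defects in the derivation, and no other section repairs them.

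**Conclusion.** The derivation is wrong as written on both counts and should be fixed. The HbA1c condition contradicts the rest of its own definition, and the form 07 and 08 conditions make membership depend on the primary outcome and possibly on allocation. The relative-risk interaction test in SAP 9.9 is therefore biased even with no true effect modification.

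The amount is not determined by the documents. With gestational diabetes assumed in 20% of live births, the false ratio of RRs is about 0.83 at a 5% baseline flag and about 0.92 to 0.97 at 20% to 80%. The second range is more likely under the HbA1c rule as it stands, when the label itself has lost its meaning. The consequence is a misleading exploratory result; the primary analysis, the BMI subgroup and the stated power are untouched.

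**What to change.** In SAP 9.4:

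1. derive the flag only from the Baseline Medical Details Form (02);
2. reverse the HbA1c inequality at the SAP's own cut-off, so that a value of 48.0 mmol/mol or above counts as yes;
3. delete the form 07 and form 08 criteria;
4. state how women with no HbA1c result are classified.

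With baseline-only criteria, a trial with no true modification gives RR 1.345 in both strata, a ratio of 1.00.

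The cost is a change of wording and one derivation, with no new data. It should be made before the trial statistician is unblinded, because a later correction could look data-driven. The drawback is that the yes group may be small (the HbA1c condition alone contributes about 3 to 122 of 1,520 women under the assumptions above) and would reflect diabetes more than insulin resistance. Label it accordingly, and report it descriptively without an interaction test if too few women qualify.
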